5.1 PERSONAL DATA

The following personal data will be collected as part of the research: Name, CHI number, study related unique identifier number, gender, age, date of birth. The data will be collected in paper and held in The Royal of Infirmary of Edinburgh and in The Royal Victoria Infirmary within a fireproof lockable cabinet within a locked room. The study data will be entered in an anonymised database where patients will be with the study related unique study identifier number (ILDHIIT001....n) held in a university computer at Centre for Inflammation Research (CIR). Personal data will be stored for 3 years. Only the research team will have access to the personal data.

No personal information will be part of the database. Patients ID will be a number corresponding to when the patient was included (i.e. first patient 001, second 002.....n). A separate file will include personal information and link this with the study ID. This separate database will be stored in an NHS computer.

5.2 DATA INFORMATION FLOW

Personal information collected will be stored in paper format and stored in the hospital under lock. Patients will be identified in the database by a study ID number (see section above) and, therefore, the database in excel format will be anonymised.

The personal data collected during approximately 6 months (stored in paper and on excel file) will be used for 6 more months and will be deleted 3 years after finishing the study. These are stored in paper (NHS facility locked room) and excel file on NHS computer.

5.3 TRANSFER OF DATA

Data collected or generated by the study (including personal data) will not be transferred to any external individuals or organisations outside of the Sponsoring organisation(s).

5.4 DATA CONTROLLER

A data controller is an organisation that determines the purposes for which, and the manner in which, any personal data are processed. The University of Edinburgh and NHS Lothian are joint data controllers along with any other entities involved in delivering the study that may be a data controller in accordance with applicable laws (e.g. the site).

5.5 DATA BREACHES

Any data breaches will be reported to the University of Edinburgh ([contact]) and NHS Lothian ([contact]) Data Protection Officers who will onward report to the relevant authority according to the appropriate timelines if required.

6. STATISTICS AND SAMPLE SIZE

We did not calculate the sample size, because this is a Randomized, Controlled, Multicentre Proof-of-Concept (PoC) study. However, we expect to recruit 30 ILD patients approximately.

Categorical variables will be summarized by frequency. Continuous variables will be expressed as mean \pm standard deviation (SD) or mean (95% confidence interval [CI]). For comparisons with the data for categorical variables or continuous variables between groups, a chi-squared test or Student's t-test will be used. The statistical analysis will be conducted with the program SPSS version 23. The level of significance for all comparisons will be set at $p < 0.05$. We will collect any adverse event information and it will only be collected on an ae log.

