3.2 SECONDARY OUTCOMES

Physical activity levels in daily life using Actigraph GT3x activity monitor, quadriceps muscle strength through the quadriceps maximal voluntary contraction test (QMVCT), quality of life using IPF-specific version of the St George's Respiratory Questionnaire (SGRQ), anxiety and depression levels through the Hospital Anxiety and Depression Scale (HADS), dyspnoea through the Modified version of the Medical Research Council scale (mMRC). The number of patients using anti-fibrotic medication will also be assessed.

Additionally, we will explore impact in blood biomarkers associated with fibrosis selected from the ELMEN study that have been shown to be associated with disease

progression (Inc. but not restricted to PAI-1, VEGF-A, PDGF-AA, PDGF-BB, Cystatin-C, Angioprotein-1, HE4/WFDC-2) (21).

We will also assess if the patients who are in treatment with antifibrotic medicines have better results than those who are not in treatment with antifibrotic medicines. This will be done in an exploratory way, where at the end of the study we will compare statistically if those patients who had a prescription of antifibrotics had better results compared to those who did not have a prescription of these medicines.

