Which group will use HFNO or conventional oxygen will be randomly selected from a sealed envelope. Randomized means that all participants will have the same chance of belonging to one group or another, they must choose a sealed envelope and inside it will be written to which group they will belong.

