4.12 DATA COLLECTION

The UK General Data Protection Regulation (GDPR) requires appropriate technical and organisational measures to be in place to implement the data protection principles effectively and safeguard individual rights. This is ‘data protection by design and by default’.

In essence, this means we will integrate or ‘bake in’ data protection into our processing activities and business practices, from the design stage right through the lifecycle.

4.12.1 Data to be collected:

- Weight
- Height
- Blood Test (blood biomarkers associated with the progression of the fibrosis)
- Blood Pressure
- QMVCT (Strength of the Quadriceps muscle measured in Newtons)
- mMRC (score of dyspnoea from 1 to 5)
- CPET (Maximum workload measured in watts)
- CWRCT (time or exercise tolerance measured in minutes)
- Physical activity levels in daily life (measured in steps)
- SGRQ (Score of this questionnaire that measures the QoL)
- HADS (Score of this questionnaire that measures anxiety and depression levels)

4.12.2 Time points for collection: these data will be collected during the baseline and post intervention appointment by the CI ([name]) and the PI ([name]) in Edinburgh and by [name] (Physiotherapist) in Newcastle.

4.12.3 Details of standardised tools to be used:

- Modified version of the Medical Research Council scale (mMRC): see appendix D.
- Saint George Respiratory Questionnaire (SGRQ): see appendix E.
- Hospital Anxiety Depression Scale (HADS): see appendix F.

4.12.4 Methods to maximise completeness of data: PI will call participants who have not returned questionnaires.

4.12.5 How will data be recorded Data will be recorded using both eCRF and pCRF.

4.12.6 Source Data Documentation: Source data is defined as all information in original records and certified copies of original records or clinical findings, observations, or other activities in a clinical study necessary for the reconstruction and evaluation of the study. Source data are contained in source documents.

Source documents are original documents, data and records where source data are recorded for the first time.

We will use the medical records from Trak to obtain information of the high resolution computed tomography (HRCT) of the thorax, echocardiograms, breathing tests including Spirometry, Lung volumes and DLCO.

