Appendix D

Modified Medical Research Council Dyspnoea Scale (mMRC): this scale goes from 0 to 5

▶ MODIFIED MRC DYSPNEA SCALE ^a		
PLEASE TICK IN THE BOX THAT APPLIES TO YOU ONE BOX ONLY Grades 0 - 4		
mMRC Grade 0.	I only get breathless with strenuous exercise.	
mMRC Grade 1.	I get short of breath when hurrying on the level or walking up a slight hill.	
mMRC Grade 2.	I walk slower than people of the same age on the level because of breathlessness, or I have to stop for breath when walking on my own pace on the level.	
mMRC Grade 3.	I stop for breath after walking about 100 meters or after a few minutes on the level.	
mMRC Grade 4.	I am too breathless to leave the house or I am breathless when dressing or undressing.	
^a Fletcher CM. BMJ 1960; 2: 1662.		

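### Section 6 offers only a chi-squared or a t-test, does not say which applies to the ordinal mMRC grade, and the protocol gives that grade three different ranges (minor)

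*Protocol*

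**What the plan says.** Section 6 sorts variables into two classes and gives a test for each: "For comparisons with the data for categorical variables or continuous variables between groups, a chi-squared test or Student's t-test will be used". It names no rank, trend or ordinal method, and it says that categorical variables are summarised by frequency. On error level: "The level of significance for all comparisons will be set at" 0.05. On size: "We did not calculate the sample size, because this is a Randomized, Controlled, Multicentre Proof-of-Concept (PoC) study", and "However, we expect to recruit 30 ILD patients approximately".

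Section 3.2 makes mMRC a secondary outcome: "dyspnoea through the Modified version of the Medical Research Council scale (mMRC"). The schedule in Section 4.11 has it at both the baseline and the post-intervention appointments.

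The scale itself is described in three ways:
- Section 4.12.1: "mMRC (score of dyspnoea from 1 to 5").
- Appendix D, opening line: a scale running from 0 to 5.
- Appendix D, the form: "PLEASE TICK IN THE BOX THAT APPLIES TO YOU ONE BOX ONLY Grades 0 - 4".

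Nowhere is mMRC classed as categorical or continuous.

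**The concern.** An ordered five-grade item falls between the two classes of Section 6, so the analyst must choose. Single-tick worded grades are naturally tabulated by frequency, which points to chi-squared. The word *score* in Section 4.12.1 points to the t-test. The two routes differ a good deal.

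A Pearson chi-squared test on the 2 × 5 table treats the grades as unordered labels. It can miss a consistent shift towards less breathlessness, and it can reach significance on a pattern with no direction. It is also poorly approximated when cells are sparse. The t-test respects the order, but as Section 6 states it, it compares groups without reference to the baseline grade. If the choice is left open, it can be made after the data are seen.

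The conflicting ranges matter separately. A recorded 1 is the second-lowest grade on the 0 to 4 form but the lowest on a 1 to 5 scale. With two sites and both paper and electronic forms, the coding needs to be fixed.

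**Working it through.** **Inputs from the protocol.** About 30 patients (Section 6). Equal chance of either group: "all participants will have the same chance of belonging to one group or another" (Section 4.1). Significance level 0.05, with two-sided testing assumed because sidedness is not stated. Five grades on the form (Appendix D).

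**Inputs that must be assumed.** The grade distribution, the effect size and the arm sizes. 30/2 = 15 per arm is only an expectation, since the 15 in Section 4.2 is per site. Without blocking, the chance of an exact 15/15 split is C(30,15)/2³⁰ = 0.14. The protocol states no power, so there is no figure of its own to reproduce.

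**Sparse cells.** With 15 per arm the mean expected count per cell is 15/5 = 3 if all five grades occur, and 15/3 = 5 if only three do. In simulation, about 60 to 90% of occupied cells had expected counts below 5 with five grades in use, and 42 to 56% with three. Under no effect, chi-squared on two of the assumed five-grade distributions rejected in about 3.3 to 3.5% of trials, against about 5% for the rank test.

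**Why order matters.** A directional test uses 1 degree of freedom; a 2 × 5 chi-squared uses 4. Take a standardised difference of 0.8. The noncentrality is n·d²/2 = 15 × 0.64/2 = 4.8. Power at that value is 59.1% with 1 df and 38.1% with 4 df, a gap of 59.1 − 38.1 = 21.0 points.

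**Simulation.** 20,000 trials per row, proportional-odds shift: odds of grade ≤ j on HFNO = OR × the control odds. For example, with 30% of controls at grade 0 or 1 and OR 3: 0.30/0.70 × 3 = 1.286, which is 1.286/2.286 = 56% on HFNO. Power in %, 15 per arm:

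| Control distribution | OR | Chi-squared | Wilcoxon | t-test | Wilcoxon minus chi-squared |
|---|---|---|---|---|---|
| 5 grades: 5/25/35/25/10% | 2 | 7.7 | 17.0 | 17.3 | 9.3 |
| | 3 | 16.3 | 35.4 | 35.6 | 19.1 |
| | 6 | 43.8 | 72.7 | 72.4 | 28.9 |
| | 8 | 57.4 | 83.9 | 83.6 | 26.5 |
| 4 grades: 15/35/35/15% | 2 | 9.9 | 17.1 | 17.6 | 7.2 |
| | 6 | 52.2 | 72.8 | 72.5 | 20.6 |
| 3 grades: 30/45/25% | 2 | 13.4 | 16.8 | 17.0 | 3.4 |
| | 6 | 57.8 | 69.3 | 68.1 | 11.5 |

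Across OR 2 to 15 the chi-squared loss is about 8 to 29 points with five grades in use and 3 to 12 with three. At 12 per arm, over OR 2 to 8, it runs from 2.4 (three grades) to 31.7 (five grades). The t-test stays within about 1.5 points of Wilcoxon throughout.

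**Baseline grade.** If the pre-post correlation is ρ, the variance of the group comparison relative to post-only values is 1 − ρ² under ANCOVA and 2(1 − ρ) for change scores. At an assumed ρ of 0.5 these are 0.75 and 1.00; at 0.7 they are 0.51 and 0.60. ANCOVA on 30 patients is then worth an unadjusted comparison on about 30/0.75 = 40 to 30/0.51 = 59. A simulation at 15 per arm with those correlations gave power of 15 to 41% for chi-squared, 31 to 63% for the unadjusted t-test and 34 to 83% for a baseline-adjusted, order-respecting analysis, over the scenarios tried.

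**The case against.** The strongest reply has four parts.

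*The protocol never sends mMRC to chi-squared.* A reader might infer that it is handled as categorical. The text does not say so. Section 4.12.1 calls it a score, in the list where SGRQ and HADS are also scores, so the t-test is at least as open a reading and loses next to nothing from ordering. This stands.

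*No single power loss belongs to this plan.* A reader might take a figure such as 15 to 28 points from simulations with five grades and large odds ratios. That needs the chi-squared reading plus a distribution and effect that the protocol does not give. Fewer grades in use is plausible: grade 4 describes someone too breathless to leave the house, or breathless when dressing, yet participants attend three times a week. This stands too, so only a conditional range can be given.

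*Dyspnoea is not measured by mMRC alone.* A reader might think it the only direct symptom outcome. Appendix E contradicts that: the SGRQ-I has a Symptoms component that includes shortness of breath, and further breathlessness items under Activities and Impacts.

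*Test choice for one secondary outcome can sit in a statistical analysis plan.* This is fair, and it keeps the point minor. It does not remove it. Section 6 does state its set of tests, and that set has no place for an ordinal outcome named in Section 3.2. The three ranges are a contradiction inside the protocol that no later document excuses.

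**Conclusion.** The point holds as a minor one. Section 6 leaves the mMRC test undetermined between two methods, neither designed for an ordered grade.

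- *If chi-squared is used*, order is discarded, most expected counts are below 5 when all five grades occur, and the loss against a rank test is roughly 3 to 29 points. This assumes 15 per arm, two-sided 5%, a proportional-odds shift with OR 2 to 15, and three to five grades in use.
- *If the t-test is used*, the loss from ordering is about 0 to 1.5 points.
- *Under either*, Section 6 makes no use of the baseline grade. A t-test on change would use it, but Section 6 does not say that change is what is compared. The size of this gain rests on an assumed correlation of 0.5 to 0.7.

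The inconsistent range (1 to 5, 0 to 5, 0 to 4) needs no assumption and is the firmest part. Nothing here touches the primary outcome, and no power claim is broken because none is made.

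**What to change.** Add to Section 6, for example: *The post-intervention mMRC grade will be compared between groups by ANCOVA (or rank ANCOVA) on group and baseline grade, with the adjusted difference and 95% CI. If the model cannot be fitted, a Wilcoxon rank-sum test on change in grade will be used. The chi-squared test will not be used for mMRC.*

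Proportional-odds regression on group and baseline grade is an acceptable alternative if sparse grades are collapsed by a rule set in advance. Its likelihood-ratio test may be anti-conservative at about 30 patients. Whichever is chosen, name one.

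State the mMRC range once and use it in Section 4.12.1, the opening line of Appendix D and the case report forms. The form itself has five boxes, 0 to 4.

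The cost is two or three sentences, with no new data, visits or patients. The downside is an effect measure slightly harder to explain than a frequency table, which can still be shown beside it.

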4.2 NUMBER OF PARTICIPANTS

15 participants with ILD will be recruited in the Lothian region, and another 15 participants in the Royal Victoria Infirmary, Newcastle upon Tyne Hospital (for

10

participants from Newcastle). The length of recruitment period will be approximately 6 months.

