4.7 BASELINE MEASUREMENTS

All the visits will take place in ward 204 (Respiratory Medicine) of the Royal Infirmary of Edinburgh (for participants from Scotland) and in the Royal Victoria Infirmary, Newcastle upon Tyne Hospital (for participants from Newcastle).

The visits during the first day before and after the intervention will take 2 hours each, and the following tests will be performed:

- Consent firstly will be re-confirmed at this visit.

- A blood test will be taken (6 ml) to know the levels of blood biomarkers associated with fibrosis that have been shown to be associated with disease progression (Inc. but not restricted to PAI-1, VEGF-A, PDGF-AA, PDGF-BB, Cystatin-C, Angiopotein-1, HE4/WFDC-2).
- A quadriceps maximal voluntary contraction test (QMVCT) will be taken to measure the strength of the quadriceps muscle.
- The shortness of breath will be assessed using the Modified version of the Medical Research Council scale (mMRC).
- Height.
- Weight.
- A Cardiopulmonary Exercise Test (CPET).
- A Constant work rate Cycle Test (CWRCT) at 75% of peak work rate (obtained from a maximal exercise test conducted beforehand) will be carried out.
- During this visit the PI will deliver to the participants the Actigraph GT3x activity monitor, which will have to be used at home for 1 week before and 1 week after of the intervention to measure the physical activity levels in daily life. The participants will have to return it during their post intervention appointment.
- Also during this visit two questionnaires called St George's Respiratory Questionnaire (SGRQ), which measure the quality of life will be delivered by the PI to be answered at home, the first one must be answered 1 day before of the intervention and returned during the first day of the intervention and the second one will have to be answered 1 day after of the intervention and returned during the post intervention appointment.
- Finally another 2 questionnaires called Hospital Anxiety and Depression Scale (HADS), which measure the anxiety and depression levels likewise will be delivered by the PI to be answered at home, the first one must be answered 1 day before of the intervention and returned during the first day of the intervention and the second one will have to be answered 1 day after of the intervention and returned during the post intervention appointment.

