5. DATA MANAGEMENT AND ANALYSIS

Data will be entered in an excel datasheet and imported to the statistical package SPSS version 23 for analysis. The anonymised database will be held in a university computer.

Physical activity level (PAL) data are handles in a standard manner: weekends are not being considered, only valid days (more than 8 h data) will be included in the analysis. At least valid data from two days need to be included as representative of valid PAL. Average of the days (minimum 2, max 5) will be the variable representing PAL. There will be different output of the monitor to include in the database (e.g. steps per day, energy consumption, etc.). Data from before the intervention and after the intervention will be generated in this manner and compared

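### Section 6 commits Tlim and the other continuous outcomes to an unadjusted t-test, without saying on post values or changes, although baselines are scheduled; baseline-adjusted ANCOVA is usually more precise

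*Protocol*

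**What the plan says.** Protocol section 6 gives the whole between-group method in one sentence: "For comparisons with the data for categorical variables or continuous variables between groups, a chi-squared test or Student's t-test will be used". It adds a common threshold ("The level of significance for all comparisons will be set at" p < 0.05). No baseline-adjusted model appears anywhere in the protocol, and centre is not mentioned in the analysis. The sentence leaves open whether post values or changes are compared.

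The baseline data are scheduled. Section 4.7 lists "A Constant work rate Cycle Test (CWRCT) at 75% of peak work rate" among the tests for the visits before and after the intervention. Section 4.1 has the post-intervention visit repeat the baseline tests apart from height, and the table in section 4.11 agrees. Quadriceps strength and blood biomarkers are taken at both visits. SGRQ, HADS and activity monitoring are done at home before and after.

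On size, the protocol says "We did not calculate the sample size" and "we expect to recruit 30 ILD patients approximately". Recruitment is split by centre: "15 participants with ILD will be recruited in the Lothian region, and another 15 participants" in Newcastle (section 4.2).

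**The concern.** When an outcome is measured before and after treatment, the baseline usually explains part of the variation in the final value. An unadjusted comparison of post values leaves that part in the error term. A comparison of changes removes it, but over-corrects when the correlation is modest. ANCOVA estimates the right amount of correction from the data.

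Two things are at stake. The first is the width of the interval for the primary estimate. With the sample held at about 30 and no power calculation, the choice of analysis is one of the few remaining ways to improve it. The second is that the protocol's wording allows either t-test, so the form of the primary comparison could be chosen after the data are seen. Naming ANCOVA closes that choice.

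**Working it through.** The protocol states no power, SD, effect size or detectable difference, so there is no figure of its own to reproduce.

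**Inputs**
- Total of about 30 patients (section 6), with equal chance of either group (sections 4.1 and 4.10). About 15 per arm is inferred. The 15 in section 4.2 is per centre.
- Alpha 0.05 (section 6), taken as two-sided because sidedness is not stated.
- Baseline-to-post correlation r: not in the protocol, so varied. SD taken as equal at both visits and set to 1.

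**Formulas, n = 15 per arm**
- Post-value t-test: SE = √(2/15) = 0.365 SD with 28 df. Half-width = 2.048 × 0.365 = 0.748 SD.
- Change-score t-test: the same SE times √(2(1 − r)), 28 df.
- ANCOVA on baseline only: the same SE times √((1 − r²)(1 + 1/26)), 27 df, t = 2.052. The term 1 + 1/26 = 1.038 is the price of estimating the slope, about 4% of variance.

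Worked example at r = 0.5: √(0.75 × 1.038) = 0.883, so the half-width is 2.052 × 0.365 × 0.883 = 0.661 SD. The ratio 0.661/0.748 = 0.884, so the interval is 12% narrower.

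**95% CI half-width (SD units) and narrowing by ANCOVA**

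| r (assumed) | Post t-test | Change t-test | ANCOVA | Narrower than post | Narrower than change |
|---|---|---|---|---|---|
| 0.2 | 0.748 | 0.946 | 0.748 | 0% | 21% |
| 0.3 | 0.748 | 0.885 | 0.728 | 3% | 18% |
| 0.5 | 0.748 | 0.748 | 0.661 | 12% | 12% |
| 0.7 | 0.748 | 0.579 | 0.545 | 27% | 6% |
| 0.8 | 0.748 | 0.473 | 0.458 | 39% | 3% |

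**Difference detectable with 80% power (noncentral t)**
- Post-value t-test: 1.06 SD at any r.
- Change-score t-test at r = 0.3 / 0.5 / 0.7 / 0.8: 1.25 / 1.06 / 0.82 / 0.67 SD.
- ANCOVA at the same r: 1.03 / 0.94 / 0.77 / 0.65 SD.

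**Where the advantage ends.** Against post values, the variances are equal when (1 − r²) × 27/26 = 1, so r² = 1/27 and r = 0.19. Allowing for the lost degree of freedom makes it about 0.20. At r = 0 the ANCOVA interval is about 2% wider. Against changes, equality is at (1 + r)/2 × 27/26 = 1, so r = 0.93, or about 0.92 with the degree of freedom. Beyond that the difference is negligible: at r = 0.95 the half-widths are 0.238 and 0.237.

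**Check.** Simulation with 20,000 trials at each of r = 0.3, 0.5 and 0.7 gave ANCOVA variance ratios of 0.94, 0.78 and 0.53 against post values. The formula gives 0.945, 0.779 and 0.530.

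All these figures adjust for baseline only. Adding centre uses one more degree of freedom, which they do not include.

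**The case against.** The strongest reply is that nothing here is invalid. In a randomised trial the t-test's interval already allows for chance imbalance, and the protocol gives no correlation from which to promise a gain. For Tlim a high correlation cannot be presumed, because each patient cycles at 75% of their own peak, which may remove some between-patient spread. That stands, and it is why the gain is given as a range: at r = 0.3 the variance falls by only about 5% against post values.

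A reader might go further than the protocol allows in several ways:
- **ANCOVA is far more precise.** This holds only against a post-value t-test and only from about r = 0.6–0.7 upward. Section 6 does not say that post values are used. If changes are compared, the narrowing at r = 0.7–0.8 is only 3–6%, and the baseline is not ignored at all.
- **Baseline imbalance in Tlim is likely.** With 15 per arm, a difference of 0.5 SD or more arises by chance in about 17% of trials (0.5/0.365 = 1.37 standard errors). That is worth guarding against, but it is not likely.
- **Every patient will have a baseline value.** Section 4.8 places randomisation before any baseline procedure, activity needs two valid days (section 5), and the questionnaires are filled in at home. A randomised patient can lack a baseline.
- **Activity will be judged by a before-after contrast.** Section 5 says "Data from before the intervention and after the intervention will be generated in this manner and compared", but that paragraph describes how the activity variable is derived. Section 6 governs comparisons between groups.

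A statistical analysis plan that is not shown may refine the method. That does not remove the point, because the protocol itself names the test.

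**Conclusion.** The point holds as a moderate one about efficiency and specification. The protocol fixes an unadjusted t-test, leaves its form open and makes no stated use of baseline values that it already schedules. The two t-tests lose precision at opposite ends: post values when r is high, changes when r is low. Because r is unknown, ANCOVA is the safer choice. It matches or beats both from r of about 0.2 up to about 0.9, and outside that range it loses at most about 2% in interval width. How much is gained depends on which t-test was meant and on r.

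The result rests on about 15 per arm, two-sided 0.05, equal SDs at the two visits and a linear relation with baseline. The t-test is not biased or wrong, and the documents do not support saying so.

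**What to change.** In section 6, make the primary analysis an ANCOVA of post-intervention Tlim on arm, baseline Tlim and centre, reporting the adjusted between-arm difference with its 95% CI. State two things in advance:
- The scale, raw or log Tlim, fixed before any outcome data are seen and not chosen from the observed skewness.
- A simple rule for randomised patients with a missing baseline, for example mean imputation of the baseline covariate, so that they are not dropped from the model.

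Use the same model for quadriceps strength, biomarkers, SGRQ, HADS and activity, and say in section 5 that activity is compared between arms.

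The cost is a paragraph of wording, with no extra patients or visits. Statistically it is one degree of freedom for baseline and one for centre, about 4% of variance for the baseline term, and a very slight loss against a post-value t-test if r is below about 0.2.

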4.8 RANDOMISATION

Following confirmation of eligibility by the CI or PI and signature of the informed consent, patients will be randomised using sealed letters to HIIT plus HFNO or HIIT plus nasal cannula. Patients will be sequentially randomised. Randomisation code and sealing of envelopes will be done by the research nurses and stored in a room at RIE and Royal

Victoria Infirmary accessible with a key. This will be done before any baseline procedures.

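### Section 6 compares the arms with a t-test that has no hospital term, although two hospitals each recruit, train and test 15 patients; adding hospital is a cheap gain in precision, not the repair of an invalid test

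*Protocol*

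**What the plan says.** Protocol section 6 names the between-arm tests: for categorical or "continuous variables between groups, a chi-squared test or Student's t-test will be used". It adds that "The level of significance for all comparisons will be set at" p < 0.05. It mentions no covariate, stratified test or hospital term, and neither does any other section.

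On the design:

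- Section 4.2: "15 participants with ILD will be recruited in the Lothian region, and another 15 participants in the Royal Victoria Infirmary" in Newcastle.
- Sections 4.1 and 4.7: all visits, training sessions and assessments alike, take place at the patient's own hospital.
- Section 4.8: the randomisation code and "sealing of envelopes will be done by the research nurses and stored in a room at RIE and Royal" Victoria Infirmary. Section 4.1 says that "all participants will have the same chance of belonging to one group or another". Blocking, stratification by hospital and separate lists are not mentioned.
- Section 4.12.2: "these data will be collected during the baseline and post intervention appointment by the CI" and the PI in Edinburgh, and by a physiotherapist in Newcastle.
- Section 3.1: the primary outcome is endurance time (Tlim) on a constant work rate cycle test at 75% of the patient's maximal workload.

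On size, section 6 says "We did not calculate the sample size, because this is a Randomized, Controlled, Multicentre Proof-of-Concept (PoC) study" and "we expect to recruit 30 ILD patients approximately". It gives no effect size, SD or power.

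**The concern.** Tlim is limited by effort. Under Appendix B the local operators urge the patient on, and under section 4.10 the training load is modified at each session to reach a target Borg score. The study is open label (section 4.9). A difference between hospitals in endurance time, or in the gain from training, is therefore plausible.

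An unadjusted two-sample test handles such a difference in one of two ways. If the arms are balanced within each hospital, the difference does not distort the arm comparison but is counted as noise, so the standard error is larger than it need be. If the hospitals are unevenly split between arms, part of the difference moves into the estimated arm effect of that particular sample. With about 30 patients, precision is scarce, and the estimate may be used to plan a later trial.

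**Working it through.** **Inputs from the protocol.** Two hospitals with 15 patients each (section 4.2), about 30 in total, Student's t-test at 0.05 (section 6), and an equal chance of either arm (section 4.1).

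**Assumptions, because the protocol gives no figure.** Two-sided test; within-hospital SD = 1; true arm effect d = 1 SD; hospital difference g = 0, 0.5, 0.75 or 1.0 SD in whatever outcome is analysed. The total of 30 has no inputs behind it, so there is no figure in the plan to reproduce.

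**Step 1: error term, closed form.** With two equal hospitals that differ by g, the variance seen by the t-test is about 1 + g²/4. At g = 0.5 this is 1 + 0.25/4 = 1.0625 (6% more); at g = 1.0 it is 1 + 1/4 = 1.25 (25% more). Noncentral-t calculations with 15 per arm (28 df for the t-test, 27 df with hospital in the model) give:

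| g (SD) | t-test power | t-test: difference detectable at 80% power | power with hospital term | with hospital term: difference detectable at 80% power |
|---|---|---|---|---|
| 0 | 75.3% | 1.06 SD | 75.2% | 1.06 SD |
| 0.5 | 72.7% | 1.09 SD | 75.2% | 1.06 SD |
| 0.75 | 69.7% | 1.13 SD | 75.2% | 1.06 SD |
| 1.0 | 65.7% | 1.19 SD | 75.2% | 1.06 SD |

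The hospital-term columns assume that hospitals are balanced across arms.

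**Step 2: chance imbalance.** The shift in the raw arm difference equals g × (difference between arms in hospital share).

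- *Simple allocation.* Exact enumeration with arm sizes from 8 to 22 gives a 36% chance that the arms differ in hospital share by 20 percentage points or more. At 20 points and g = 0.5, the shift is 0.5 × 0.20 = 0.10 SD.
- *Unrestricted 15:15 allocation* (hypergeometric 30, 15, 15). A 9:6 split by hospital, or worse, has probability 46.6%; 9:6 gives 9/15 − 6/15 = 0.20, so a shift of 0.20g. A 10:5 split, or worse, has probability 14.3%; 10:5 gives a shift of 0.33g.

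**Step 3: simulation of both tests.** The outcome is d × arm + g × hospital + N(0,1). The t-test is compared with a linear model on arm and hospital, under two allocation schemes.

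| g (SD) | Simple: t-test power | Simple: with hospital | Balanced within hospital: t-test power | Balanced: with hospital | Balanced: t-test type I error |
|---|---|---|---|---|---|
| 0 | 74% | 72% | 75% | 75% | 5.0% |
| 0.5 | 71% | 72% | 73% | 75% | 4.4% |
| 0.75 | 68% | 72% | 70% | 75% | 3.8% |
| 1.0 | 64% | 72% | 67% | 75% | 3.1% |

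Under simple allocation the type I error of the t-test is about 5% at every g. The balanced scheme puts 7 and 8 patients of one arm at the two hospitals, and its power is averaged over which arm gets the odd patient. At g = 1.0 the two orientations give about 73% and 60% for the t-test; the hospital-adjusted model gives 75% in both.

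**Net effect of the hospital term on power, in points.** Simple allocation: −2 / +1 / +4 / +8. Balanced within hospital: 0 / +2 / +5 / +8.

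**The case against.** The strongest reply is that both analyses are valid, so the choice between them is one of efficiency. This stands. A reader might infer from the missing hospital term that the trial risks too many false positives, or that the arm comparison is biased. The documents do not support that. Over repeated randomisation the t-test holds its level or falls below it, and the shift in step 2 is conditional on one realised imbalance.

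A reader might also infer that patients are randomised separately within each hospital. Section 4.8 says only that the envelopes are stored at both hospitals and that patients are randomised in sequence; separate or stratified lists are not stated. The point does not depend on it: balanced lists leave hospital in the error term, and unstratified ones admit chance imbalance.

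No hospital difference can be sourced, and several features work against a large one: written test procedures (Appendices A and B), a test load set at 75% of each patient's own maximum, training load individualised to a Borg target, and one saturation target for both arms. This stands too, and it is why the figures are shown as a range starting at zero. Different staff make a difference possible; they do not make 0.75 to 1 SD likely.

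Section 6 does not say whether post-training values or changes are tested. If changes, a constant difference in level between hospitals cancels, and g must be read as a difference in gain, which may be smaller. This limits the size, although local training and testing can still produce a difference in gain.

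Finally, covariates are often left to an SAP, which is not at hand. But section 6 does not leave the matter open: it names the test.

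**Conclusion.** The point holds as a modest improvement. Section 6 fixes an unadjusted comparison in a design where hospital is a clear source of variation. The hospital term gains about 1 to 2 power points at a 0.5 SD hospital difference and about 8 points at 1 SD, and loses about 0 to 2 points if the hospitals do not differ. It also removes the shift from an uneven hospital split, which is small (0.10 SD at a 20-point imbalance and a 0.5 SD hospital difference).

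These figures rest on an assumed arm effect of 1 SD, assumed hospital differences, 15 patients per hospital, and no dropout. The stated test is not wrong, and its overall false-positive rate is not inflated. Priority is moderate to low; the low cost is the main reason to act.

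**What to change.** In section 6, replace the t-test for Tlim and the other continuous outcomes with a linear model containing arm and hospital (two levels), and report the hospital-adjusted arm difference with its 95% CI. The same model serves whether post-training values or changes are analysed.

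The chi-squared test needs no stratified replacement: the listed outcomes are almost all continuous or ordinal scores, and antifibrotic use is the only clearly binary item.

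Cost: one sentence and one degree of freedom (27 instead of 28). No new data or patients are needed.
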